2.3.2 Known Potential Benefits

In general, individuals may have some transient benefits, such as increased subjective sensation of energy, mood and cognitive function.

Single KE drink dose studies have shown improved glycemic response to OGTT [39](#) and decreased ghrelin and hunger [32](#); these effects which might be beneficial for our study population which consists of individuals with MetS. However, those benefits might not be clinically important since, in a 28-day study on the KE, there was no change in weight and glucose parameters [25](#).

In healthy rats, a KE-diet improved their physical activity when compared with carbohydrate or Western type of diet [13](#). In high-performance athletes, co-ingestion of KE with carbohydrates significantly increased their cycling performance compared with carbohydrates only [37](#). Those results indicate that KE might be beneficial for the endurance level of any human and especially of those who exercise.

As with physical activity, healthy rats showed improved cognition while on the KE supplement [13](#). In AD animal models, KE administration resulted in cognitive improvement, anxiety reduction and decreased brain pathology [12,14](#). The cognitive effects of KE have never been tested systematically in humans, although there is one case reported in literature in which KE subjectively improved cognition in AD [10](#). Therefore, it is possible that the KE-group in our study might experience a transient boost in cognition and mood while on the KE drink.

The positive effects described above were described for the period during which the animals or individuals were on the intervention; thus, the potential benefits refer to short-term benefits only. No potential long-term benefits are currently known.

2.3.3 Assessment of Potential Risks and Benefits

Known side effects of consuming KE are common GI tract side effects such as nausea. These have been systematically assessed mainly in studies of 1, 4, 5 or 28 days [24,39,40](#) [23,25,26,32,36-38](#). Importantly, it has been shown that when KE is ingested with water, it is well tolerated, especially when the dose is ~ 25 g per drink. The most common GI side effect is mild nausea, which is still very rare (occurred in 6 out of 2,016 total drinks in one study) [25](#). In one study authors reported frequent GI effects, but these were attributed to large amounts of milk that the supplement was co-administered with [36](#). Since the GI side effects may partially be explained by the bitterness of the KE drink, we will advise participants to drink some water immediately after the drink to mask the bitterness of the supplement.

The terms “ketones”, “ketosis”, “ketogenic” should not be confused with “ketoacidosis”, a complication of Diabetes Mellitus during states of a profound imbalance between insulin availability and requirements (e.g. during infection, or insulin dose skip). Studies performed in healthy individuals have shown that KE supplementation decreases PH, sometimes in the range of normal PH and other times at levels of mild acidosis [24,26](#). Importantly, in one of those studies, the KE supplementation did not have any effect on PH during maximal exercise intensities despite decreased PH before exercise [24](#). However, supplementation with KE drinks is not comparable to Diabetic Ketoacidosis, since KE can increase blood ketones only to a certain degree (which is known to be safe) and they drop to baseline within 4 hours [25](#). Thus, ketosis induced with KE drinks is transient and not uncontrolled. On the other hand, insulin deficiency in DKA creates a potentially uncontrollable state that will not reverse until insulin requirements are met. Our study population will be individuals meeting criteria for MetS which include fasting plasma glucose ≥ 100 mg/dL or drug treatment for high blood glucose [41](#). However, as an additional layer of safety, we will not

include individuals with DM and thus eliminate any possibility of a participant developing ketoacidosis due to complete insulin deficit.

KE and Placebo drinks will be isocaloric. In both groups, individuals will consume $140 \times 3 = 420$ calories derived from the supplement, per day. For both groups, we don't expect any changes in systemic metabolic parameters from this amount of calories and that duration of study. Notably, KE has been shown to decrease hunger and ghrelin after a single dose [32](#). However, in a 28-day study on the KE drink there was no change in glucose, cholesterol, TGs and body weight [25](#). The placebo will contain dextrose (DXT). Importantly, we will exclude diabetics from the study; therefore, any metabolic risk from receiving a supplement containing DXT will be minimal. For a typical diet of 2000-2500 calories/day, the 420 calories from either KE or DXT will constitute ~20% of the daily calories. We believe that participants will self-regulate reducing their food intake given the intake of these extra calories from the supplement.

The value of the information to be gained from this study outweighs the potential risks for the following reasons:

- The risks are minimal.
- Individuals may have some transient benefits, such as increased subjective sensation of energy, mood and cognitive function.
- Most importantly, the study will provide proof of concept on whether oral KE supplementation can robustly increase brain availability of ketones, in a population relevant to AD in terms of brain IR and brain glucose hypometabolism. It will also provide evidence for the effects of this intervention on neuronal metabolism and AD-related cascades (as reflected on EV biomarkers of IR, autophagy, and AD). Additionally, the study will provide information on the cognitive effects of KE, measured with a sensitive neuropsychological battery.
- Ultimately, this study could become a “bridge” towards a future clinical study on the effects of KE in AD. The importance of this is potentially profound, as there is no effective treatment of AD.

3 OBJECTIVES AND ENDPOINTS

OBJECTIVES	ENDPOINTS	JUSTIFICATION FOR ENDPOINTS
Primary		
To investigate the change in brain concentration of BHB, using brain MRS, after 28 days of supplementation with the KE drinks compared to baseline and placebo.	To detect with brain MRS, a significant change in the concentration of BHB, after 28 days of supplementation with KE drinks compared to baseline and placebo.	A previous study on a different ketogenic intervention (MCTs) given to individuals with AD, showed that the combined AcAc and BHB CMR measured globally or at specific

OBJECTIVES	ENDPOINTS	JUSTIFICATION FOR ENDPOINTS
		regions (frontal lobe, parietal lobe, temporal lobe, occipital lobe, cingulate cortex, subcortical regions) with PET scan, was significantly increased. With this ketogenic intervention there was also improvement in only 3 out of the 23 different cognitive tests ⁶ . We expect to demonstrate a change in brain BHB with KE using brain MRS, a technique that measures concentration rather than CMR.
Secondary		
To assess whether genetic factors modulate the response to the KE supplement.	To assess whether genetic factors modulate the response to the KE supplement.	In a previous randomized clinical trial of 5:2 Intermittent Fasting versus Healthy Living diet in older individuals with insulin resistance, we showed that the diets had differential effects on induction of peripheral ketosis based on genetic polymorphisms for the SLC16A7 and APOE genes. ³⁵ We expect to find similar differential effects on induction of peripheral and, by extension, brain ketosis in response to the KE supplement.
Exploratory		
i) (a) To investigate the acute effects (single dose) of KE drink on brain BHB measured with brain MRS, compared to	i) (a) To detect with brain MRS, a significant change in the concentration of BHB, acutely after single dose of KE drink, compared to	i) (a) and (b): We have shown higher Glucose/Creatine and Lactate/Creatine

OBJECTIVES	ENDPOINTS	JUSTIFICATION FOR ENDPOINTS

baseline and placebo; (b) To investigate the acute (single dose) and chronic effects (28 days on intervention) of other brain metabolites measured with MRS, compared to baseline and placebo); (c) similarly, to investigate with MRS, chemical changes in the thigh muscle at rest, during and after exercise, reflecting mitochondrial function.
 
ii) To investigate the acute (single dose) and chronic (28 days) effects of KE drinks intake compared to baseline and placebo, on blood and urine BHB
	
baseline and placebo. (b) To detect with brain MRS, a significant change in the concentration of other metabolites (glucose, lactate etc), acutely after single dose, and chronically after 28 days on the KE drink compared to baseline and placebo. (c) To look with 31P MRS (optional) for changes in intramuscular pH, ATP and Creatine Phosphate in the thigh muscle, acutely after a single dose, and chronically after 28 days on the KE drink compared to baseline and placebo.
 
ii) Blood will be drawn before and after a dose of KE drink or Placebo, during Visits 2,3 and 4. Urine will be collected during Visits 2 and 4 (over ~8 hours).
	
concentration in the precuneus of AD patients compared to younger and older cognitively normal participants 2. Decreasing these parameters suggests improved brain metabolism, with less reliance on glycolysis, which is linked to AD pathogenesis 42. (c) In animal models treated with ketogenic diets or BHB, there is greater energy production from ATP hydrolysis, improved mitochondrial biogenesis, metabolomics changes and changes in muscle morphology 12,43,44. We will use 31P MRS to study changes in muscle bioenergetics with KE drinks, which may provide additional broad insights on the effects of ketones on cellular metabolism and health.
 
ii) With the exception of one human 28-day study, all studies on KE drinks have been conducted for a period of 5 or fewer days. Importantly, the 28-day study was designed as single-arm study without control group 33. Thus, the present study will confirm the efficacy of KE drinks in terms of inducing ketosis, by measuring BHB in blood and urine.

OBJECTIVES	ENDPOINTS	JUSTIFICATION FOR ENDPOINTS

iii) To investigate the chronic (28 days on intervention) effects of KE drinks intake on plasma EV biomarkers related to insulin signaling and resistance and autophagy, neuronal and astrocytic ketone metabolism, AD pathogenic cascades, compared to baseline and placebo.
 
iv) To investigate the acute (single dose) and chronic (28 days) effects of KE drinks intake compared to baseline and placebo on cognitive performance by using scalable
	
iii) EV endpoints:
 
 • Similar total levels and increased levels of activating phosphorylations at the level of IR, IRS-1, IGF1R, canonical cascade (Akt, GSK3B, S6K), alternative/mitogenic cascade (MAPK, JNK, p38), and mTOR/p-mTOR • Increased levels of MCT-1 and 2, and other enzymes facilitating ketone metabolism • Elevation of NAD⁺/NADH ratio • Aβ40, Aβ42, p181-tau and total tau • Complement and other neuroinflammatory mediators • Markers for diverse AD pathogenic processes (such as lysosomal dysfunction, cellular stress responses, and other factors that may be identified in the future) • RNA species involved in AD pathogenesis. 
iv) PACC total composite z-score and NIH toolbox cognitive composite score
	
iii) These EV-based biomarkers have shown significant moderate magnitude differences between active and placebo groups in previous clinical trials assessing metabolic interventions 45,46. These measures are expected to change in association with change with brain BHB measured by MRS, serum BHB, and cognitive performance.
 
iv) These composite scores assess cognition globally and contain measures sensitive to detect changes in this cognitively normal population.

OBJECTIVES	ENDPOINTS	JUSTIFICATION FOR ENDPOINTS

and challenging cognitive measures with relevance to AD.
 
v) To investigate the chronic effects of 28 days of KE drinks compared to baseline and isocaloric placebo supplement on gut microbiota and intestinal permeability
	
v) Stool samples will be subjected to microbiome analysis by RNA sequencing to determine changes in bacterial species composition between and within groups.
	
v) Diet has a significant impact on gut microbiota.⁴⁷ Short-chain fatty acids such as butyric acid are the natural end-product on non-digestible carbohydrate fermentation by the gut microbes and has been shown to regulate ketone body metabolism during the fasted state in mice.⁴⁸ In addition, ketogenic diets have been reported to produce changes in gut microbiota, and differences in gut microbiota profile after ketogenic diet treatment have been reported between responder and non-responder in epileptic patients.^{49,50} Furthermore, age-associated changes in gut microbiota promote intestinal barrier impairment and subsequent systemic inflammation and metabolic dysfunction in mice.⁵¹ Therefore, we also plan to investigate whether a KE drink has effects on gut microbiota and intestinal permeability.

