1 PROTOCOL SUMMARY

1.1 SYNOPSIS

Title:	Ketone ester effects on biomarkers of brain metabolism and cognitive performance in cognitively intact adults ≥ 55 years old. A double-blinded randomized controlled clinical trial.
Study Description:	We hypothesize that supplementation with a ketone ester drink [Ketone Ester (KE)] compared to placebo, in cognitively intact adults ≥ 55 years old with Metabolic Syndrome (MetS), will (i) increase peripheral and brain ketone levels [primarily β -hydroxybutyrate (BHB) and secondarily acetoacetate (AcAc)], (ii) improve neuronal/astrocytic insulin resistance (IR) and induce a change in neuronal/astrocytic metabolism as reflected on blood Extracellular Vesicle (EV) biomarkers, (iii) improve cognitive performance, (iv) boost mitochondrial function in muscle, and (v) change gut microbiome. These effects will be examined acutely, after single-dose administration, and chronically, after 28 days on the supplement x 3 times per day. The changes in EV biomarkers and cognition will be associated with the elevation of ketones in brain. The study will involve a Screening Visit and three additional Visits to assess acute effects, compliance and chronic effects, respectively, and a follow-up visit to obtain DNA.
Objectives:	
Primary: To investigate the change in brain concentration BHB, using brain Magnetic Resonance Spectroscopy, after 28 days of supplementation with the KE, compared to baseline and placebo.
 
Secondary: To test the hypothesis that genetic factors may affect the response to the KE supplement.

Endpoints:	
Primary: To detect with brain MRS, a significant change in the concentration of BHB, after 28 days of supplementation with the KE compared to baseline and placebo
 
Secondary: To assess whether genetic factors modulate the response to the KE supplement.

Study Population:	Males or females, of age ≥ 55 years who meet the criteria for MetS and are cognitively intact.
Phase:	N/A – study of a dietary supplement.

Abbreviated Title: Oral Ketone Ester effects on brain function

Version Date: 10/29/2024

Description of Sites/Facilities

Enrolling Participants: The study will take place at a single site, at the NIA Clinical Unit at the Medstar Harbor Hospital, Baltimore

[figure not shown]
Description of Study Intervention: Oral KE drink [containing 25 g KE/(R)-3-hydroxybutyl (R)-3-hydroxybutyrate] vs isocaloric Placebo drink (containing dextrose) x 3 times/day x 28 ± 3 days

Study Duration: 25 months

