1.3 SCHEDULE OF ACTIVITIES (SOA)

Procedure	Pre-Visit phone Screen	Visit 1	Visit 2	Visit 3	Visit 4	Visit 5
		Screening	Baseline assessments – first dose – acute effects assessments	Compliance Assessment	Last dose. Chronic effects assessments	
Timing			Within 28 days of V1 Day 1 on supplement	Day 14 (+/-3 days) on supplement	Day 28 (+/-3 days) on supplement	
Informed Consent		X				X
Screening of Inclusion/Exclusion Criteria	X	X				
Demographics		X				
Medical History		X				
Review of concomitant medications		X	X	X	X	

Abbreviated Title: Oral Ketone Ester effects on brain function
Version Date: 10/29/2024

Physical Exam		X			X	
Vital signs		X	X	X	X	
Nursing assessment		X	X	X	X	
Anthropometric measures [Height (cm), Weight (kg), waist circumference (cm or in)] *Height to be measured during V1 only. Weight and waist circumference to be measured during V1 and V4.		X			X	
Blood draw for screening clinical labs: See section 8.2.5		X (fasting)				
Blood draw for clinical labs and EV biomarkers. See section 8.2.5			X (fasting/before supplement)	X (fasting/before supplement)	X (fasting/before supplement)	
Blood draw for DNA collection (for genetic studies): See section 8.2.5						X
Serum β -hydroxybutyrate			X (fasting and ~60 min after supplement)	X (fasting and ~60 min after supplement)	X (fasting and ~60 min after supplement)	
Stool samples			X (within 24 h before the visit)		X (within 24 h before the visit)	
Urine BHB			X (collected during the visit)		X (collected during the visit)	

Abbreviated Title: Oral Ketone Ester effects on brain function
Version Date: 10/29/2024

Urine drug screen		X				
Urine Pregnancy test		X	X	X	X	
Cognitive assessment for eligibility (CDR, MOCA)		X				
Randomization (after eligibility determined) by NIA Pharmacist		X				
Ketone Ester or Placebo dispensed by NIA pharmacist			X (first of three daily doses received in-house)	X (first of three daily doses received in-house)	X first of three daily doses received in-house)	
Self-administration of Ketone Ester or Placebo x 3 times per day			Throughout the 28-day period			
MRI/MRS Brain			X (before and ~75 min after supplement)		X (before and ~75 min after supplement)	
Optional Thigh MRS			X (before after supplement)		X (before and after supplement)	
Outcome cognitive testing			X (before the supplement)		X (~ 2.5 h after the supplement)	
Review compliance logs of drinks				X	X	
Modified Credibility/Expectancy Questionnaire				X	X	

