8.2.2 Neuropsychological Assessment

Cognitive testing will be administered by a study investigator during the screening, baseline and final visits (Visits 2 and 4). Screening cognitive testing will consist of screening tests that are commonly used to ascertain normal cognitive status: participant-informed Clinical Dementia Rating (CDR) scale (global score = 0) and Montreal Cognitive Assessment (MoCA) (≥ 26). For deriving efficacy measures, we will use a battery modeled after the preclinical Alzheimer cognitive composite (PACC [57](#)), which includes the Free and Cued Selective Reminding Task (FSCRT) for list learning, the Logical Memory task for episodic memory, the Digit-Symbol task for timed executive function, the MoCA as a global cognitive measure, and an overall Z-transformed composite score. In addition, attention, episodic memory, working memory, language/fluency, and executive function, and their composite score will be assessed via the NIH Toolbox (www.nihtoolbox.org [58](#)); a comprehensive, psychometrically sound, and well-validated computerized testing battery that reliably and uniformly assesses cognitive function. Cognitive

testing will take place before the supplement intake at Visit 2 (baseline) and ~3 hours after supplement intake at Visit 4 to assess acute on chronic effects.

8.2.3 Magnetic Resonance Spectroscopy (MRS)/Magnetic Resonance Imaging (MRI):

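### No cognitive test follows the first dose, so the acute cognitive objective has no data and the 28-day effect can be estimated only together with that day's dose

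*Protocol*

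**What the plan says.** **What is promised.** Objective iv (Protocol section 3) is "To investigate the acute (single dose) and chronic (28 days) effects of KE drinks intake compared to baseline and placebo on cognitive performance". The synopsis (section 1.1) lists cognition as its third expected effect and then says of the whole list: "These effects will be examined acutely, after single-dose administration, and chronically, after 28 days on the supplement x 3 times per day". The hypothesis in section 4.1 covers acute and chronic administration and includes better cognition as item iii.

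**What is measured.** The Schedule of Activities (section 1.3) places outcome cognitive testing before the drink at Visit 2 and about "2.5 h after the supplement" at Visit 4. Section 8.2.2 gives the times as "before the supplement intake at Visit 2 (baseline) and ~3 hours after supplement intake at Visit 4 to assess acute on chronic effects". Section 8.3 confirms the outcome battery (PACC and NIH Toolbox) at Visits 2 and 4. No section schedules a test after the drink at Visit 2 or before it at Visit 4.

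**What the rationale says.** Section 4.3 justifies the 28 days by acute and chronic effects on brain BHB, but lists cognition only under chronic effects.

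**What the SAP says.** It labels cognition exploratory and gives no time points, contrast or model for it. The Group, Time and interaction model is written for the primary endpoint. The SAP hypothesis on cognition says only that performance will improve, with no acute claim.

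**The concern.** Objective iv names two effects and compares each with both baseline and placebo. The schedule supports less. An acute effect needs a test after the first dose, and there is none. The one follow-up test comes 2.5 to 3 hours after a drink, and section 2.3.3 says ketones return to baseline within 4 hours of a dose. The Visit 4 result therefore cannot show whether any benefit outlasts the last drink. That distinction matters because section 2.3.2 anticipates a transient boost in cognition, and sections 2.1 and 2.3.3 present the study as a bridge to a trial in Alzheimer's disease.

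The comparison with baseline adds a second difficulty. Within the ketone ester arm, change from Visit 2 to Visit 4 mixes any product effect with practice on a repeated battery and with the change from pre-dose to post-dose testing. The MoCA, part of the PACC-type battery, is also given at screening, so by Visit 4 it has been taken three times.

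**Working it through.** The plan has no figure for this point. Its sample size (25 per arm for d = 0.80, two-sided alpha 0.05, power 0.80) reproduces and is not in dispute: n = 2(1.960 + 0.842)²/0.80² = 24.5, rounded up to 25 per arm, with power 0.807 by the normal approximation and 0.791 by the t-test. The check here is which effects the scheduled tests can estimate.

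**Notation for mean scores**
- m: the pre-dose mean at Visit 2, equal in both arms by randomisation
- t: retest practice and the passage of time to Visit 4
- s: being tested after a drink rather than before one, as seen with the dextrose placebo
- A: effect of a single ketone ester drink relative to a placebo drink
- C: effect of 28 days of ketone ester relative to placebo, apart from that day's dose
- I: any interaction of A and C

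**Planned tests** (Protocol sections 1.3, 8.2.2 and 8.3)

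| Test | Placebo | Ketone ester |
|---|---|---|
| Visit 2, pre-dose | m | m |
| Visit 4, post-dose | m + t + s | m + t + s + A + C + I |

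**Contrasts available**
- Change within the ketone ester arm: t + s + A + C + I
- Change within the placebo arm: t + s
- Difference between the two: A + C + I

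The between-arm difference is free of t and s. The within-arm change is not. Neither A nor C can be obtained alone, whether or not I is set to zero. A matrix-rank check on these cells gives the same answer: A not estimable, C not estimable, the sum estimable.

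**What separation would need**
- A post-dose test at Visit 2 has means m + s and m + s + A, so the arm difference is A.
- A pre-dose test at Visit 4 has means m + t and m + t + C, so the arm difference is C.
- With no interaction (I = 0), either extra test is enough, making 3 tests per participant. With an interaction, both are needed, making 4. The plan has 2.

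**Comparison with the other endpoints.** Where the protocol claims acute and chronic effects elsewhere, it samples for both. Brain MRS is done before and after the drink at Visits 2 and 4, and serum BHB before and after it at Visits 2, 3 and 4. The extracellular vesicle objective (iii) claims only chronic effects, and its blood is drawn only before the drink. Cognition is the mismatch.

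**Timing.** The schedule and section 8.2.2 differ by 3 − 2.5 = 0.5 h. Both times fall inside the 4-hour window of section 2.3.3.

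**The case against.** The strongest reply is that the chronic objective is answered. The synopsis defines chronic as after 28 days on the supplement, and the schedule labels Visit 4 as the chronic-effects visit. In a randomised, double-blind trial the Visit 4 comparison with placebo is a fair estimate of the regimen. This stands. A reader might infer from the schedule that the chronic cognitive question cannot be answered at all, but the documents do not support that: no section promises an effect measured off the dose, and section 8.2.2 openly describes the test as serving "3 hours after supplement intake at Visit 4 to assess acute on chronic effects". What is lost is only the separation of 28 days' use from that day's drink.

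A second reply is that objective iv compares with baseline and placebo, so the placebo arm deals with practice. That is true of the between-arm contrast. It does not cover a within-arm claim, and the SAP does not say which comparison decides the cognitive conclusion. The Group-by-Time interaction would also be a valid between-arm contrast, but it is not written for cognition.

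Third, the harm is limited. With no post-dose test at Visit 2, no acute cognitive estimate can be produced. The remaining risk is that the Visit 4 result is read as answering both halves of the objective.

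Finally, a reader might infer that the half-hour discrepancy means a materially different ketone level at testing. The documents give no decline curve that would show this, only a return to baseline within 4 hours. Both times are approximate and apply to both arms, so this is an inconsistency to reconcile and not a bias.

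**Conclusion.** The point holds in a limited form. The acute single-dose cognitive effect in objective iv, the synopsis and section 4.1 item iii has no assessment behind it, and sections 4.3 and 8.2.2 do not match that claim. The 28-day effect is validly estimable against placebo, but only as a combined effect that includes that day's dose. Two effects are claimed; one contrast, A + C + I, is estimable. Change from baseline within an arm should not carry the conclusion.

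This rests on the schedule as written and on practice and post-dose testing conditions acting alike in the two arms, which randomisation and blinding are there to secure. No assumption about ketone kinetics is needed for the estimability result. The consequence is confined to an exploratory endpoint. The primary MRS measure is taken before and after the drink at both visits and is untouched.

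**What to change.** - **Protocol sections 1.1, 3 (objective iv) and 4.1 (item iii):** remove the acute single-dose claim for cognition. State one acute-on-chronic cognitive effect of the 28-day regimen, measured on-dose, consistent with sections 4.3 and 8.2.2. The numbered statistical hypotheses in Protocol 9.1 and the SAP make no acute cognitive claim and need no change on that account.
- **SAP, Exploratory Analyses:** base the cognitive conclusion on the ketone ester versus placebo contrast at Visit 4, adjusted for the Visit 2 score. Report within-arm change descriptively only.
- **Protocol sections 1.3 and 8.2.2:** reconcile the Visit 4 test time so that both give the same one.

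The cost is wording and a narrower exploratory claim; the Visit 2 score is already collected and no testing is added. If the sponsor wishes to keep separate acute and chronic cognitive claims, the missing tests in the working would have to be added, at the price of participant time and further retesting.
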